### 6.11 Peri – procedural anticoagulation

Heparin should be administered prior to or immediately following transseptal puncture during AF ablation procedures and adjusted to achieve and maintain an ACT of 300 to 400 seconds.

Performance of AF ablation in subjects systemically anticoagulated with warfarin does not alter the need for intravenous heparin to maintain a therapeutic ACT during the procedure.

Administration of protamine following ablation to reverse heparin may be considered.

### 6.12 Renal angiography

Perform renal angiography if randomized to Treatment, following the pulmonary vein isolation procedure.

Subjects should be prepped for a renal angiography according to standard procedures. For subjects with chronic kidney disease and/or risk factors for contrast-induced nephropathy (CIN), the hospital's standard-of-care protocol for CIN prevention should be utilized.

An aortogram and selective renal angiography will be performed to confirm renal artery anatomy. Anatomic eligibility is defined as each kidney having at least one renal artery  $\geq 3$ mm and  $\leq 8$ mm in diameter and minimum treatable length per the Symplicity Spyral Catheter Instructions for Use, without significant stenosis or other abnormality. *NOTE: All renal arteries with  $\geq 3$  mm and  $\leq 8$ mm diameter with minimum treatable length per the Symplicity Spyral Catheter Instructions for Use shall be*

*treated, including dual renal arteries meeting these morphologic criteria.*

### **6.13 Renal artery denervation procedure**

If randomized to Treatment, the renal artery denervation procedure will be performed according to the supplied Symplicity Spyral Catheter Instructions for Use, Symplicity G3 Generator User Manual and associated training provided by Medtronic.

Prior to this procedure, appropriate systemic anticoagulation and sedation should be attained. Blood pressure and heart rate should be closely monitored throughout the procedure. Investigators may choose to apply treatment to any renal artery that meets the anatomy eligibility criteria. The Symplicity Spyral Catheter will be delivered to the renal artery and the ablation treatments at multiple positions along the renal artery will be performed according to the procedures described in the Instructions for Use.

Provide one copy of the renal angiogram cine procedure to Medtronic.

Sedation type, procedure information, fluoroscopy time, contrast dye amount and concentration will be collected.

### **6.14 LINQ insertion**

Before the subject is discharged from the hospital, preferable while still in the EP lab, insert the Reveal LINQ device. The insertion procedure will be performed in accordance with the hospital's standard practice and in accordance with the Medtronic Reveal LINQ manual. Program Device Data Collection parameters and verify device sensing performance is acceptable. Subjects with an existing Reveal LINQ device may be enrolled if they have a minimum of 1 year remaining battery life. Ensure the device is programmed to the settings below.

#### *6.14.1 Programming Requirements*

Required programming:

Parameter	Required Setting
Reason for Monitoring	AF ablation
Type of AT/AF detection	AF only
AF Detection	Balanced sensitivity
AT/AF Record of ECG of	All episodes
Ectopy Rejection	Nominal

Recommended programming:

Parameter	Required Setting
Tachy detection	OFF
Brady detection	OFF
Pause detection	OFF

Perform a device interrogation and data transfer (e.g. save-to-disk, USB data transfer) with the final programmed settings. Final interrogation may be performed at hospital discharge. Ensure, at a minimum, Medtronic receives an interrogation with the final programmed settings.

## 6.15 Device deficiencies

A device deficiency is defined as inadequacy of a medical device with respect to its identity, quality, durability, reliability, safety or performance. NOTE: Device deficiencies include malfunctions, use errors and inadequacy in the information supplied by the manufacturer including labeling. Device deficiencies that do not adversely affect the subject should be reported to Medtronic as a device deficiency and not as an adverse event. If the device deficiency is a reportable adverse event, the event should be reported as an adverse event not a device deficiency. Report device deficiencies for all Medtronic products used.

## 6.16 Hospital discharge

Prior to discharge, the following shall be collected: blood and urine samples, assess medications, assess adverse events, and review study requirements with the subject to help ensure compliance with follow-up procedures.

The use of CareLink will then be reviewed and training will be given prior to discharge to the subject.

Systemic anticoagulation with warfarin or a direct thrombin or Factor Xa inhibitor is recommended for at least two months following the AF ablation procedure.

Decisions regarding the continuation of systemic anticoagulation agents more than two months following ablation should be based on the subject's risk factors for stroke and not on the presence of AF. Discontinuation of systemic anticoagulation therapy post ablation is not recommended in subjects who are at high risk of stroke as estimated by currently recommended schemes (CHADS2 or CHA2DS2VASc).

## 6.17 Scheduled follow-up visit windows

After receiving notice of a subject pulmonary vein isolation procedure, Medtronic will provide the target dates and windows to complete each visit either to the center, in-home, virtually or by phone. Should a subject visit fall outside the pre-specified window, a study deviation must be reported, and the original follow-up schedule maintained for subsequent visits.

Data analyses include data collected at late and early follow-up visits. Therefore, a late or early visit is preferred over a missed visit but must be accompanied by a deviation. Subjects will be followed until all subjects who underwent a pulmonary vein isolation procedure reach the 6-month visit.

Table 6: Follow up visit windows

Study Follow-up Visit	Window (Calculated days post-procedure attempt)		
	Window Start (# of days)	Target (# of days)	Window End (# of days)
1 month	30	30	46
6 month	180	180	194
12 month	335	365	395
18 month	515	545	575
24 month	700	730	760
30 month	880	910	940

36 month	1065	1095	1125
42 month	1245	1275	1305

Additional windows will be sent to centers if they extend beyond 42 months.

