## 6.18 Scheduled in-office follow-up visits

### 6.18.1 One, Six and Every Six Month Visit Until Study Closure

It is recommended that anti-hypertensive medications and dose not be changed through the 6 month visit unless medically necessary. It is recommended that subjects be off all antiarrhythmic medications within 90 days post cryoablation procedure.

The following will be collected:

- blood and urine samples (not required after the 6 month visit)
- physical exam
- vital signs (including 3 blood pressure measurements according to Appendix G: Blood Pressure Measurement Procedures)
- review of medications
- assess for adverse events
- assess arrhythmias and symptoms, episodes of medical care suggestive of arrhythmia including hospitalizations, office or ER visits, or any AF-related procedures such as cardioversions or additional ablations
- interrogate the Reveal LINQ device, review prior CareLink reports and the current interrogation for possible AF related events

Alternative methods of data collection may be necessary in the case of extenuating circumstances, such as a global pandemic, when subjects are prohibited from coming into the office for required assessments. For all assessments completed via alternative methods in these circumstances, sites are not required to enter a protocol deviation for missing, alternative, and/or late data collection. Data unable to be collected remotely or via an alternative method should be collected at the next possible in-person visit.

In the event a subject is unable to return for an in-office follow-up visit, the alternative methods of obtaining follow-up assessments are listed below:

- In-home visit by trained and delegated site personnel or designee, i.e. home health care personnel. The following assessments may not be completed with an in-home visit:
  - CareLink in-office interrogation. Guide a subject through a full interrogation (“Interrogate All”) at the end of the follow-up visit
  - Renal Artery Imaging:
    - Make every effort to schedule in-person renal artery imaging as soon as possible.

When possible, subjects may be referred to a local imaging center for assessment. Local imaging technicians would require study training and delegation prior to assessment. In the event an in-home visit is not possible, the alternate methods for obtaining follow-up assessments are listed below:

- Virtual Visit, i.e. inclusive of video with study subject.

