  - The following assessments may not be completed with a virtual visit:
    - Physical examination, limited review to be completed per physician discretion.
    - CareLink in-office interrogation. Guide a subject through a full interrogation (“Interrogate All”) at the end of the follow-up visit.
    - Laboratory Tests:
      - When possible, the subject should be referred to a local laboratory to collect samples. Laboratory Kits to be provided to subjects in advance of the visit by study site.
    - Renal Artery Imaging:
      - Make every effort to schedule in-person renal artery imaging as soon as possible.
      - When possible, the subjects could be referred to a local imaging center for assessment. Local imaging technicians would require study training and delegation prior to assessment.
  - Office blood pressure unit to be provided to the subjects in advance of the visit by study site. Measurements collected by the patient may be collected and designated in the case report form.
- Phone visit, i.e. no video with the subject.
  - The following assessments may not be completed with a phone visit:
    - Physical examination limited review to be completed per physician discretion.
    - CareLink in-office interrogation. Guide a subject through a full interrogation (“Interrogate All”) at the end of the follow-up visit
    - Laboratory Tests:
      - When possible, the subject should be referred to a local laboratory to collect samples. Kits to be provided to subjects in advance of the visit by study site.
    - Renal Artery Imaging
      - Make every effort to schedule in-person renal artery imaging as soon as possible.
      - When possible, the subjects could be referred to a local imaging center for assessment. Local imaging technicians would require study training and delegation prior to assessment.
  - Office blood pressure unit to be provided to the subjects in advance of the visit. Measurements may be collected and designated as patient reported in the case report form.

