#### *12.3.5 Analysis Methods*

For computing the proportion of subjects in each arm that experience safety composite events, Kaplan-Meier methods will be used. Since all components of the safety composite event include events through 30 days and four components include events through 6 months post-procedure, there is the potential for some subjects having incompletely assessed safety composite outcomes should they discontinue study participation prior to 6 months of post-procedure follow-up.

Kaplan-Meier estimation uses the time that each subject is free from a safety composite event, defined from the date of procedure to the earliest date that an

event meeting one of the safety composite event component definitions occurs. For events that are typically confirmed at a clinic visit (e.g. renal artery stenosis confirmed with angiography), it can be difficult to determine the onset date exactly. Therefore, events whose onset date is equal to a follow-up visit date within the 6-month visit window will be treated as having occurred at 180 days post-procedure. All subjects that are event-free through a completed 6-month follow-up visit within the 6-month visit window will be censored at 180 days. Otherwise, a subject's event-free time will be from the date of procedure to the latest follow-up visit. Treating safety composite event dates and censoring dates that occur at 6-month visits within the 6-month visit window as occurring at exactly 180 days post-procedure prevents bias in the Kaplan-Meier 6-month estimate. The log-log transformation will be used to calculate a two-sided 95% confidence interval for the rate of safety composite events within each study arm.

The difference in event rate between arms will be estimated by the difference in Kaplan-Meier estimates at 6 months. A 95% confidence interval for the difference will be constructed by applying the delta method to the log-log transform of the difference in the Kaplan-Meier estimates.

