A randomized design was selected to compare safety and effectiveness between subjects receiving both renal artery denervation and pulmonary vein isolation within one procedure (Treatment arm) and subjects receiving only pulmonary vein isolation (Control arm). The randomized design will help minimize biases and control for confounding factors between comparison groups. Subjects and center personnel will be blinded to the randomization assignment until after the pulmonary vein isolation procedure.

Statistical Analysis Plan Purpose

This Statistical Analysis Plan (SAP) documents, before data is analyzed, the planned analyses that will be included in the Symplicity AF final report. Additionally, reports and analysis created for the Data Monitoring Committee (DMC) will use this SAP for guidance. Analyses for Symplicity AF publications will not be limited to this SAP.

This plan does not limit the analysis that may be provided in reports or publications.

The Symplicity AF Clinical Investigation Plan (CIP) version 12, dated 24/JUN/2016, was used to develop the SAP. Version 16 of the CIP, dated 23/MAY/2018, was used to update the SAP, largely to reflect the inclusion of an interim analysis.

4. Study Objectives

Primary Objectives

1. Safety: The primary safety objective characterizes the rate of safety composite events within each of the two study arms and also characterizes the difference in the rates between study arms.
2. Effectiveness: The primary effectiveness objective compares the rate of chronic treatment success between study arms.

Secondary Objective

1. The secondary effectiveness objective characterizes the rate of chronic treatment success in Treatment and Control arms in the subgroup of subjects that do not undergo an additional pulmonary vein ablation procedure during the 90 day blanked follow-up period.

Ancillary Objectives

The ancillary objective endpoints below will be compared between study arms in order to further characterize the differences in outcomes between patients randomized to pulmonary vein isolation only to those randomized to pulmonary vein isolation and renal artery denervation.

1. Office systolic and diastolic blood pressure at 6 months compared to baseline
2. Heart rate at 6 months compared to baseline
3. Procedural measures (total procedure time, cryoablation procedure time, renal artery denervation procedure time, ablation time, fluoroscopy time, dye usage)
4. Symptoms at 6 months compared to baseline

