  TIME time*event(0);
  TEST trtGroup;
RUN;
```

Other code may be needed to analyze the difference in event rates between arms.

Explanation of variables

- trtGroup (treatment group):
 - Equals 1 if subject randomized to the treatment arm
 - Equals 0 if subject randomized to the control arm
- Event
 - Equals 1 if subject experienced a component of the primary safety endpoint during follow-up on or before the 6-month visit
 - Equals 0 if a subject did not experience a component of the primary safety endpoint during follow-up on or before the 6-month visit
- Time (from procedure date to first event or censor in days)
 - If Event = 1

- Determine the earliest date that a component of the primary safety endpoint was experienced for each subject
 - If the earliest event onset date is equal to a follow-up visit date within the 6-month visit window, then Time equals 180 days
 - If the earliest event onset date is prior to the subjects 6-month visit window, then Time equals the earliest date that a component of the primary safety endpoint was experienced minus the date of procedure
- If Event = 0 (censor)
 - and the 6-month follow-up visit was completed within the 6-month visit window, then Time equals 180 days
 - and the 6-month follow-up visit was not completed, then Time equals the date of the latest visit prior to the 6-month visit minus the date of procedure

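### The primary safety rule can score a denervated subject as free of renal artery stenosis to day 180 after a remote 6-month visit without renal imaging, and it gives no way to score a stenosis first dated on deferred imaging

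*Protocol*

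**What the plan says.** **Visit mode.** Protocol 6.17: "Medtronic will provide the target dates and windows to complete each visit either to the center, in-home, virtually or by phone". Section 6.18.1 reserves the alternatives for subjects who cannot attend, for example in a pandemic.

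**Imaging at those visits.** Renal artery imaging appears under all three lists in 6.18.1: "The following assessments may not be completed with an in-home visit", "The following assessments may not be completed with a virtual visit" and "The following assessments may not be completed with a phone visit". Sites are to try to arrange in-person imaging as soon as they can and may refer the subject to a trained local imaging center. Data that cannot be collected remotely go to the next possible in-person visit. No deadline is given, and "sites are not required to enter a protocol deviation for missing, alternative, and/or late data collection".

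**Role of the imaging.** The 6-month duplex ultrasound is done only in denervated subjects and triggers angiography (Protocol 6.18.1.1). New renal artery stenosis is a safety composite component with a 6-month onset interval, defined as above 70% and confirmed by angiography (Protocol 12.3, Table 11 and 12.3.1.5).

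**Scoring.** Protocol 12.3.5: "All subjects that are event-free through a completed 6-month follow-up visit within the 6-month visit window will be censored at 180 days". The SAP 7.10.1.4 event flag "Equals 1 if subject experienced a component of the primary safety endpoint during follow-up on or before the 6-month visit".

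**Versions.** The SAP introduction states: "Version 16 of the CIP, dated 23/MAY/2018, was used to update the SAP". The protocol's change history places the alternative follow-up methods in version 17.

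**The concern.** The scoring rule uses attendance at the 6-month visit as evidence that all 6-month components were assessed. When the visit could only be held in person, the ultrasound normally came with it. With remote visits the two can separate, and the SAP was last aligned with a protocol version that predates them.

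Stenosis is the component most specific to denervation, and the 6-month ultrasound is its only scheduled screen. Subjects who were not screened stay in the day-180 denominator as event-free. Because Control has no scheduled renal imaging, the effect runs one way: it favors Treatment in both the arm-specific rate and the between-arm difference. Protocol 12.3.3 says these estimates will guide the design of a pivotal study, and SAP 7.10.1.4 draws a 5%-level conclusion from the interval for the difference.

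**Working it through.** **1. The plan's own figure.** Protocol 12.3.4 expects a composite rate of 4.5% to 9.2% when both procedures are done. This is the sum of the two source rates, 3.1% + 1.4% = 4.5%, and of their upper bounds, 6.3% + 2.9% = 9.2%. Both reproduce.

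**2. One subject traced through SAP 7.10.1.4.** Take a denervated subject whose 6-month visit is a phone call on day 185, inside the 180 to 194 window of Table 6, with no imaging yet.

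- No event reported: Event = 0. If the call is a completed visit, Time = 180, censored.
- Stenosis later confirmed, with onset dated to the deferred imaging: the onset falls after the 6-month visit, so the flag is not set. The Time rules for events cover only an onset on a visit date inside the 6-month window, or before the window. Neither applies.
- Stenosis later confirmed, but onset adjudicated to before the window: the event would count. Nothing tells the adjudicators when to do this.

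**3. Safeguards.** SAP 7.4 plans no imputation. Its tipping-point procedure converts only subjects censored before the estimation time point, so it does not reach those censored at day 180. The deviation waiver means the deviation log need not show who was not imaged.

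**4. Size, as an illustration.** Inputs: 70 subjects at 1:1 (Protocol 12.1 and 6.9), so 35 in Treatment. Let m be the number not imaged by any route in time and x the stenoses found among those imaged. The documents give neither, so both are assumed. Assume also no other events or dropout.

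- Planned rule: x/35.
- Imaged subjects only: x/(35 − m).
- Share of true stenoses detected, if equally likely in imaged and unimaged subjects: 1 − m/35.
- One-sided 95% upper limit with zero stenoses among n subjects: 1 − 0.05^(1/n), with n = 35 − m.

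| m | Planned, x = 1 | Imaged only, x = 1 | Share detected | Upper limit, x = 0, imaged only |
|---|---|---|---|---|
| 0 | 2.9% | 2.9% | 100% | 8.2% (n = 35) |
| 4 | 2.9% | 3.2% | 89% | 9.2% (n = 31) |
| 7 | 2.9% | 3.6% | 80% | 10.1% (n = 28) |
| 11 | 2.9% | 4.2% | 69% | 11.7% (n = 24) |
| 18 | 2.9% | 5.9% | 49% | 16.2% (n = 17) |

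The upper limits show how much information on stenosis is lost. They are not a planned output, which is a two-sided log-log Kaplan-Meier interval for the whole composite.

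**5. Expected loss.** Suppose all of the 1.4% denervation composite rate in Protocol 12.3.4 were stenosis. Then m = 7 hides 7 × 0.014 = 0.10 events, or 0.10/35 = 0.3 points, and m = 18 hides 18 × 0.014 = 0.25 events, or 0.7 points. If one stenosis does occur in this group and is not counted, the loss is 1/35 = 2.9 points.

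**The case against.** - **No text says that a remote visit is a completed visit for safety censoring.** This is correct. It is inferred from 6.17, which supplies windows for completing visits in those modes, and from the absence of a definition. The supportable claim is that the rule is undefined here and, followed literally, gives the result above.
- **Deferred does not mean missed.** This also stands. Local referral or a separate in-person appointment may produce an image within the window, and the problem then disappears for that subject.
- **A late-found stenosis is not necessarily dropped.** A reader might infer that the plan excludes every stenosis found after the visit. The documents do not go that far. The composite uses onset, the event flag refers to when a component was experienced, and the events committee classifies subjects. Such a stenosis would also appear in the adverse event listing. What stands is that one dated to the deferred imaging has no scoring branch.
- **The stakes are limited.** The safety objective has no hypothesis and no performance requirement, and the effectiveness boundaries are untouched. Sensitivity analyses are not limited to tipping point, although the one described would miss these subjects.

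**Conclusion.** The gap is real, and its direction is certain: missed screening can only lower the detected Treatment rate and the between-arm difference. Its size is not known. It depends on how many denervated subjects had no renal imaging by any route in time, and it is nil if there were none. At the denervation rate cited in the plan, the expected loss is a fraction of a point (0.3 points for 7 unimaged, 0.7 for 18). A single uncounted stenosis would be 2.9 points, against an expected composite rate of 4.5% to 9.2%.

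This rests on reading a remote in-window visit as completed, on 35 Treatment subjects, and on assumed unimaged counts. It does not show that the safety estimate is wrong by any stated amount, and no pass/fail decision depends on it. It should still be settled before the safety analysis, because the repair is cheap and the estimate is meant to inform a pivotal design.

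**What to change.** 1. In SAP 7.10.1.4 and Protocol 12.3.5, count an angiographically confirmed stenosis found on deferred 6-month imaging as an event at day 180, up to a prespecified analysis cut-off. One option is before the 12-month window opens at day 335.
2. Keep all observed follow-up for the other components. Do not censor unimaged subjects at the preceding visit, which is month 1. That would discard about five months of observation on the other 6-month components and make censoring depend on outcome. For example, take one day-100 event in an unimaged subject, with the other unimaged subjects censored at month 1. With 7 unimaged the estimate becomes 1/(35 − 6) = 3.4%, and with 18 it becomes 1/(35 − 17) = 5.6%, against an observed 1/35 = 2.9%.
3. Report the number of denervated subjects with evaluable 6-month renal imaging beside the Treatment rate, and give the stenosis component with imaged subjects as the denominator.
4. Extend the missing-data sensitivity analysis in SAP 7.4 to unimaged denervated subjects credited to day 180.

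The cost is a few sentences in each document, a derived variable for imaging status and date, and a little more analysis work. No new study procedure is needed. The downside is that a stenosis that arose shortly after 6 months may be counted; the cut-off limits this.
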